### **9.6.Treatment accounting and compliance**

Study medication should be stored in a safe place with limited access, under the conditions established in the investigator's brochure. The medication will be labelled with the study protocol code, batch number, content, expiry date, storage conditions, investigator and name of the sponsor.

The monitor will supervise the study medication in the hospital pharmacy prior to destruction, after accounting for the medication has been completed. Medication accounting will be documented and amounts shipped, dispensed, returned and destroyed will be verified.

All unused medication provided by the sponsor will be destroyed at each participating site and properly documented. If requested by the sponsor, unused medication will be returned to the sponsor.

All study drug inventory forms should be available for inspection by authorised representatives of the sponsor or by health authority inspectors. The investigator is responsible for counting all used and unused study supplies at their site.

### **9.7.Prohibited drugs**

Concomitant administration of interleukin-6 receptor inhibitors and immunomodulatory drugs is not permitted.

Concomitant use of chloroquine and derivatives is not permitted.

Patients may receive other pharmacological treatments for COVID-19 at the discretion of the investigator after 24 hours from the administration of the last dose of plitidepsin.

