### **9.2. Dosage and administration**

Patients included in the study will be randomised in a 1:1:1 ratio to receive:

- Arm A) 1.5 mg of plitidepsin administered as a 1.5-hour infusion, once a day for 3 consecutive days.
- Arm B) 2.0 mg of plitidepsin administered as a 1.5-hour infusion, once a day for 3 consecutive days.
- Arm C) 2.5 mg of plitidepsin administered as a 1.5-hour infusion, once a day for 3 consecutive days.

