  - 9 The first time the patient tested positive for COVID-19 will be included as well. The test will be repeated in the 48 hours prior to administration of plitidepsin and on days 4, 7, 15 and 31, if negative detection does not occur before then. Qualitative PCR shall be obtained on nasopharyngeal exudate (preferably) or a sample from the lower respiratory tract.
  - 10 A chest X-ray will be performed at baseline and subsequently based on clinical discretion.
  - 11 Only fertile women.
  - 12 Patients may receive other pharmacological treatments for COVID-19 at the discretion of the investigator 24 hours after administration of the last dose of plitidepsin.
  - 13 Adverse events (serious and non-serious) will be recorded from signing of the informed consent up to 28 days after administration of the last dose of plitidepsin.
  - 14 A safety visit will be made 28 days (+3 days) after the last dose of plitidepsin.
  - 15 The viral load should be determined in a sample obtained from nasopharyngeal exudate (preferably) or a sample from the lower respiratory tract.

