## **12.5. Analysis of secondary endpoints**

### **12.5.1. Efficacy assessments**

Efficacy analyses will be performed on the efficacy population defined above. For the evaluation of efficacy endpoints, the following analyses will be carried out separately for each dosage level:

- The evolution of the viral load from the baseline visit on days 3, 4, 7, 15 and 31 will be provided.
- The time to negative detection of COVID-19 by PCR will be calculated as the time that elapses in days from the date of randomisation to the first date of PCR with a negative result. The time to negative detection will be analysed following the Kaplan-Meier methodology, providing the median and the corresponding 95% confidence interval.
- The number and percentage of patients who die 7, 15 and 31 days after starting the treatment with plitidepsin shall be described.
- The number and percentage of patients who require mechanical ventilation and/or ICU admission at 7, 15 and 31 days will be provided.
- The number and proportion of patients requiring invasive mechanical ventilation shall be stated.
- The number and proportion of patients requiring non-invasive mechanical ventilation shall be stated.
- The number and proportion of patients requiring oxygen therapy shall be stated.

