8.1 Efficacy evaluation

The following tests will be performed to evaluate the efficacy of the treatment:

a) Viral load evolution:

For the analysis of the evolution of the viral load, the number and percentage of patients from who a sample has been collected will be indicated to determine the viral load at baseline and at visit 4, 7, 15 and 31 describing the results in those patients (number of RNA copies detected and log of the number of copies). The result will be given to three decimal places.

The graphs of the evolution of the viral load (mean and median) of the patients from the baseline to the last visit will be presented. These graphs will be shown by separate for each dose level, by FDA baseline classification and Oxygen support or not on day 1.

In addition, the following variables will be analyzed:

- The number and percentage of patients who viral load result is maintained, decreased or increased with respect to the previous visit on days 4, 7, 15 and 31 will be presented.
- Negative detection (global and by dose level):
- The number and percentage of patients with negative or undetectable viral load on days 4,7,15 and 31.
- The number and percentage of patients with negative or undetectable viral load on days 4,7,15 and 31 in the subgroups of low, medium and high initial viral load.
- Time to negative detection (viral load 0 or undetectable) in overall patients from date of PCR at baseline.
- Time to negative detection (viral load 0 or undetectable) based on baseline viral load (high (>7 copies/mL) / medium [4-7 copies/mL] / low (<4 copies/mL)) and other baseline characteristics (sex, age, race, ...) will be explored.
- Time to negative detection based on corticosteroid treatment (<10 days vs > 10 days)
- Viral load (high, medium, low) will be correlated with study outcome variables such as need for oxygen therapy, admission to ICU (Yes / No), NIMV, IMV, days of hospitalization, death (Yes / No).

- Determine the relationship between the number of days with symptoms and having a higher or lower viral load.
- Determine the relationship between viral load and the baseline situation of the patient, mild-moderate-severe, oxygen need / no need.
- The relationship between viral load and different inflammatory parameters (LDH, ferritin, C-reactive protein, D-dimer and lymphocytes) will be graphically analyzed.
- The mean change in viral load log₁₀ RNA copies/mL from baseline to day 4, 7, 31 will be analyzed in:
 - All patients

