9.6 Other COVID-19 treatments

The listing “Other COVID-19 treatments” will include the following information including the baseline visit

- Center
- Patient id.
- Treatment arm (Arm A; Arm B; Arm C)
- COVID-19 Pharmacological treatment (Yes/No). If so, it will be described:
 - Chloroquine / Hydroxychloroquine (Yes / No).
 - Tocilizumab (Yes/No).
 - Remdesivir (Yes/No).
 - Lopinavir/Ritonavir (Yes/No).
 - IFN B 1b (Yes/No).
- Other pharmacological treatment (Yes/No). If so, a list per patient will be provided.
- Support treatment (Yes/No). If so, it will be described:
 - Antibiotics (Yes/No). If so, it will be described:
 - Azitromizina (Yes/No).
 - Other (Yes/No). If so, the specific treatment will be described
 - High-dose corticosteroids (excluding pre-medication) (Yes/No). If so, the specified treatment description will be described.
 - Antifungal agents (Yes / No). If so, the description of the specified treatment will be described.
 - Other support treatments (Yes / No). If so, the description of the specified treatment will be described.

Note: Information will only be provided for those patients receiving other COVID-19 drug treatment and/or supportive treatment at those visits where indicated.

The active substances provided will be coded including code (ATC) and term indicated in the database.

In the case of another pharmacological treatment for COVID-19 and/or support treatment with high-dose corticosteroids drugs, information about the time, in days, since the start of treatment with plitidepsin and the start of the other therapy, and the duration of the treatment will be provided

For corticosteroids, the daily dose received data will also be provided.

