High >7				
Total				

Table 12.1.11 Time to negative detection

Time to negative detection	Time to negative detection			p-value(**)
	N	Median	Range	
Viral load at baseline				
Low <4				
Medium [4-7]				
High >7				
Dose				
1.5 mg				
2.0 mg				
2.5 mg				
Age				
< 65 y.o.				
>=65 y.o.				
Sex				
Female				
Male				
Race				
White				
Other				
... (*)				

(*) FDA risk groups (Mild, moderate, severe), Oxygen need (Yes/No), Chronic lung disease (Yes/No), Corticosteroids (Yes/No), Other antiviral treatment for COVID-19 (Yes/No). Further variables could be added upon request

(**) Kruskal-Wallis

Table 12.1.12 Time to negative detection by corticosteroid duration

Time to negative detection	Corticosteroid duration		p-value*
	< 10 days	>= 10 days	
Dose			
1.5 mg			
2.0 mg			
2.5 mg			
Total			

(**) Kruskal-Wallis

Table 12.1.13 Oxygen therapy

Number of patients (%)	Dose Cohort							
	1.5 mg N=X		2.0 mg N=X		2.5 mg N=X		Total N=X	
	Oxygen therapy							
	Yes	No	Yes	No	Yes	No	Yes	No
Oxygen therapy at baseline								
Yes								
No								
Chronic Lung Disease								
Yes								
No								
Age								
< 65 y.o.								
>=65 y.o								
Gender								
Female								
Male								
Race								
White								
Other								
Viral load at baseline								
Low <4								
Medium [4-7]								
High >7								
FDA Risk groups								
Mild								
Moderate								
Severe								

Listing 12.1.14 Oxygen therapy evolution

Subject id	Dose	Visit	Date	Time	Oxygen therapy type	Flow

Table 12.1.15 Oxygen therapy onset day

Onset day	Dose Cohort							
	1.5 mg N=X		2.0 mg N=X		2.5 mg N=X		Total N=X	
From start of symptoms								
From first plitidepsin dose								
From corticosteroids use								

Table 12.1.16 Patients changing oxygen therapy

	Dose Cohort			
	1.5 mg N=X	2.0 mg N=X	2.5 mg N=X	Total N=X
From no Oxygen therapy to Oxygen therapy				
From low flow to high flow				
From high flow to low flow				

Table 12.1.17 Time in (ICU- Invasive M Ventilation – Non Invasive MV – in Hospital)

Time (days)	Dose Cohort			
	1.5 mg N=X	2.0 mg N=X	2.5 mg N=X	Total N=X
ICU				
Invasive mechanical ventilation				
Non Invasive mechanical ventilation				
Hospital*				

(*)From first infusion

Table 12.1.18 Reason for ICU discharge

Endpoint	Dose Cohort			
	1.5 mg N=X	2.0 mg N=X	2.5 mg N=X	Total N=X
Reason for ICU discharge, n (%)				
Taken back to the ward				
Death				

Table 12.1.19 ICU admission according to oxygen therapy or chronic lung disease

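### Only the Day 4 viral sample is largely free of other antivirals; viral load change at Days 7, 15 and 31 and later time to negative PCR are exposed, with no sensitivity analysis

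*Protocol*

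**What the plan says.** **Dosing.** Protocol 9.2 gives each arm one infusion a day for three days, for example "1.5 mg of plitidepsin administered as a 1.5-hour infusion, once a day for 3 consecutive days". The calendar in Protocol 10 places these on Days 1, 2 and 3.

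**Other drugs.** Protocol 9.7 states: "Patients may receive other pharmacological treatments for COVID-19 at the discretion of the investigator after 24 hours from the administration of the last dose". Footnote 12 of the calendar repeats the rule: "at the discretion of the investigator 24 hours after administration of the last dose of plitidepsin".

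**Viral sampling.** The calendar has viral load and PCR at baseline and on Days 4, 7, 15 and 31. Footnote 9 has the PCR repeated "on days 4, 7, 15 and 31, if negative detection does not occur before then". Neither footnote 9 nor footnote 15 (viral load) says whether the Day 4 sample comes before or after another COVID-19 drug started that day.

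**Analysis.** Protocol 12.5.1 says: "The evolution of the viral load from the baseline visit on days 3, 4, 7, 15 and 31 will be provided". SAP 8.1 a) uses Days 4, 7, 15 and 31 and adds: "The graphs of the evolution of the viral load (mean and median) of the patients from the baseline to the last visit will be presented". Table 12.1.7 gives the mean change by dose.

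**Handling of other antivirals in the SAP.**
- SAP 8.1 c) relates the PCR outcomes to use of other antivirals or other specific treatments.
- Table 12.1.11 has a yes/no row for another antiviral.
- SAP 9.6 lists, for each patient, the number of days from starting plitidepsin to starting the other therapy.
- Table 11.8.3 shows use of other COVID-19 treatment by dose.

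Starting a permitted drug is not a ground for withdrawal (Protocol 8.1) and does not affect the efficacy population (Protocol 12.3, SAP 4.1).

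**The concern.** Viral load change and time to negative PCR head the list of efficacy measures, and the efficacy data are to be weighed with safety when the dose for the next trial is chosen. Protocol 5.2 calls the trial uncontrolled, and masking does not apply (Protocol 7.4). The treating investigator knows the dose and decides whether to add another drug. If other antivirals are started more often at one dose than at another, the faster viral decline that they cause enters that dose's mean, and Table 12.1.7 cannot separate the two. The same problem affects the time-to-negative curve after Day 4. It also affects the planned figures in SAP 15.2 that set plitidepsin beside remdesivir, since remdesivir is one of the drugs recorded in SAP 9.6.

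**Working it through.** **1. Day numbering.** Protocol 6.1 equates 12 days after the end of treatment with day +15. With the last dose on Day 3, 3 + 12 = 15, which agrees. The safety visit 28 days after the last dose gives 3 + 28 = 31, which also agrees. The same count puts the 24 h opening at 3 + 1 = Day 4.

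**2. Time open to other drugs before each sample.** Let the first infusion start at 0 h. The third starts at 48 h, so the window opens at 72 h, or at 73.5 h if the 24 h run from the end of the 1.5 h infusion. A sample on Day d at the same clock time falls at (d − 1) × 24 h. Hours open = sample time − opening time.

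| Sample | Hours since first dose | Hours open | Share open |
|---|---|---|---|
| Day 4 | 72 | 0 | 0% |
| Day 7 | 144 | 70.5–72 | 49–50% |
| Day 15 | 336 | 262.5–264 | 78–79% |
| Day 31 | 720 | 646.5–648 | 90% |

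An assumed worst case for Day 4 is an 08:00 infusion on Day 3 and a swab at midnight at the end of Day 4. That leaves 16 h open, or 16 − 1.5 = 14.5 h counted from the end of the infusion.

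**3. Time to negative.** Three of the four scheduled post-baseline PCR tests (Days 7, 15 and 31) fall after the opening.

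**4. What a shift could look like (assumed values only).** Suppose a share f of an arm starts another antiviral as soon as it is allowed, and this adds b log10 copies/mL of decline per day over t days. The arm mean shifts by f × b × t. With f = 10–50% and b = 0.1–0.5:
- Day 7 (t = 3): 0.1 × 0.1 × 3 = 0.03, up to 0.5 × 0.5 × 3 = 0.75 log10.
- Day 4, worst case (t = 16/24): 0.1 × 0.1 × 16/24 = 0.007, up to 0.5 × 0.5 × 16/24 = 0.17 log10.

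These are shifts in one arm. A false dose difference needs unequal use: (f1 − f2) × b × t. The plan has 15 patients per dose, so three users in one arm and none in another is 3/15 = 20 percentage points. At Day 7 this gives 0.2 × 0.1 × 3 = 0.06, up to 0.2 × 0.5 × 3 = 0.30 log10. Equal use with equal effect cancels.

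**5. Why the existing split is weak.** It groups patients by something that happens after baseline. A patient who clears the virus early has less time and less reason to start another antiviral. Users will therefore tend to show longer times to negative whatever the drug does, and a yes/no row does not show whether it was started before or after clearance.

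**6. Day 3.** A Day 3 viral load would precede the window. It is named in Protocol 1.11, Protocol 12.5.1 and SAP 2.6, but is absent from Protocol 6.3, the calendar and SAP 8.1.

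**The case against.** A reader might infer that no viral endpoint is protected, because all four scheduled samples fall on or after the day the window opens. The documents do not support this. Under the 24 h rule a Day 4 swab taken by the 24 h mark has no permitted exposure, and a late one has hours.

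A reader might also infer that the yes/no row in Table 12.1.11 is the SAP's only safeguard. It is not. SAP 8.1 c) plans a wider breakdown, SAP 9.6 gives the start day of other therapy, and Table 11.8.3 would reveal unequal use between doses. Nor does the drug list in SAP 9.6 show that these drugs are expected. It includes chloroquine and tocilizumab and also covers baseline, so it reads as a checklist.

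It is fair to add that viral load is a secondary, descriptive endpoint and that natural decline already prevents attribution to plitidepsin in an uncontrolled trial. That limits what any analysis can claim, but the comparison between doses remains and is the one unequal use would distort.

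Two objections to the remedy also stand. Dropping values after another drug starts conditions on a post-baseline event. And the SAP listings record a start day, not a clock time, so the order of events on Day 4 may not be recoverable.

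**Conclusion.** The concern holds in limited form. Day 4 is largely free of other antivirals, though the plan does not secure the swab order. Viral load change at Days 7, 15 and 31 is exposed for about 50%, 79% and 90% of the time since first dose, and so is time to negative PCR after Day 4. Mean viral load change has neither a split nor a sensitivity analysis for other antivirals. The split for PCR outcomes ignores timing.

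The size of any bias is unknown, because the documents do not report actual use. The log10 figures above rest on assumed uptake and effect and show scale only. The timing result assumes that footnote 12 governs. The calendar row for other COVID-19 treatments appears to be marked from Day 2, which may only denote data collection and should be clarified. This is a worthwhile improvement to secondary endpoints that inform dose selection; it does not touch the primary safety analysis.

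**What to change.** - **Protocol 10, footnotes 9 and 15:** state that the Day 4 swab is taken before the first dose of any other COVID-19 treatment given that day, without delaying that treatment.
- **SAP 8.1 a) and c):** keep the planned analyses. Add, as a sensitivity analysis, a version of Table 12.1.7 and of the time-to-negative curve using only data before the first other antiviral. Where only a date is known, state in advance how same-day starts on Day 4 are treated.
- **Day 3 viral load:** reconcile Protocol 1.11, Protocol 12.5.1 and SAP 2.6 with Protocol 6.3, the calendar and SAP 8.1, in line with what is actually collected. The direction is for the sponsor to decide.

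**Cost.** One sentence on sampling order, one repeated table and one repeated curve. The start day of other therapy is already listed. The added version has fewer values at Days 7 to 31. Its censoring may be informative, because patients given other drugs may have a different course, so it should be read beside the planned analysis and not replace it. The figures in SAP Appendix V already carry counts for 6 + 23 + 16 = 45 patients. If sampling is complete, the swab-order sentence comes too late and the sensitivity analysis with its same-day rule is the part that can still be used.

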### **9.8.Drug interactions**

There have been no clinical studies on drug interactions.

If the patient is already under treatment with chloroquine or one of its derivatives and given its arrhythmogenic potential, the patient may not be included in the study.

#### **Effect of other medicinal products on plitidepsin**

##### **Interactions with CYP3A4 inhibitors and inducers**

In vitro studies indicate that CYP3A4 is the major enzyme involved in plitidepsin metabolism, followed by CYP2A6 and CYP2E1. However, a pharmacokinetic population analysis of plitidepsin including 283 patients indicated that concomitant administration of CYP3A4\* inhibitors and inducers does not affect exposure to plitidepsin [12]. However, it cannot be ruled out that concomitant treatments that inhibit or induce CYP3A4 may modify the efficacy and/or increase the probability of side effects associated with plitidepsin, so they should be avoided.

- Co-administration with CYP3A4 inhibitors and inducers should be avoided, as they may affect the plasma concentration of plitidepsin.
- Co-administration with CYP3A4 inhibitors and moderated inducers should be used with caution, as an effect on plitidepsin exposure cannot be excluded.

### **Interactions with CYP3A4 inhibitors**

Plitidepsin should not be administered with potent inhibitors CYP3A4 (e.g. grapefruit juice, clarithromycin, itraconazole, nefazodone, telithromycin, voriconazole). Potent inhibitors CYP3A4 should be discontinued before starting treatment and during treatment with plitidepsin. They may be re-administered 24 hours after the last dose of plitidepsin.

Moderate inhibitors CYP3A4 (e.g., aprepitant, diltiazem, erythromycin, fluconazole, verapamil) should be used with caution, as increased exposure to plitidepsin cannot be excluded

### **Interactions with CYP3A4 inducers**

To avoid a decrease in the effectiveness of plitidepsin, plitidepsin should not be administered with potent inducers of CYP3A4 enzyme, such as anticonvulsants (phenytoin, phenobarbital or carbamazepine), rifampicin, rifabutin and St. John's wort, unless there are no therapeutic alternatives. The appropriate initial dose for patients taking potent inducers has not been defined. They may be administered again 24 hours after the last dose of plitidepsin.

CYP3A4 moderate inducers (e.g. bosentan, modafinil, nafcillin) should be used with caution, as a reduction of exposure to plitidepsin cannot be excluded.

A list of CYP3A4 inducers and inhibitors is included in Annex 5.

### **Effect of plitidepsin on other drugs**

In vitro studies did not show a potential for plitidepsin to inhibit or induce metabolism of other drugs. However, the results for ruling out the potential inducing effect of plitidepsin on the CYP2B6 enzyme were inconclusive. The potential effect of plitidepsin on CYP2B6 has not been studied in vivo.

Therefore, decreases in plasma concentrations of drugs that are substrates of this enzyme cannot be ruled out when co-administered with plitidepsin.

## 10. EVALUATION CALENDAR

	Baseline	Day 1	Day 2	Day 3	Day 4	Day 5	Day 6	Day 7	Day 15 (± 1 day)	Day 31 (± 3 days) 
Informed consent 	X									
Selection criteria 	X									
Medical record	X									
Vital signs 	X	X	X	X	X	X	X	X	X	X
Demographics	X									
Physical examination	X									
Electrocardiogram 	X	X	X	X	X	X	X	X	X	X
Complete blood count 	X	X*	X	X	X	X	X	X	X	X
Biochemistry 	X	X*	X	X	X	X	X	X	X	X
Coagulation 	X	X*	X	X	X	X	X	X	X	X
C-reactive protein 	X	X*	X	X	X	X	X	X	X	X
Viral load 	X				X			X	X	X
PCR COVID-19 	X				X			X	X	X
Chest x-ray 	X	Based on clinical criteria								
Pregnancy test 	X									
Treatment		X	X	X						
Other pharmacological treatments for COVID-19 			X	X	X	X	X	X	X	X
Adverse events 	X	X	X	X	X	X	X	X	X	X

- \* It will not be necessary to repeat the tests on day 1 if they were carried out in the 24 hours prior to administration of plitidepsin.
- 1 The patient will sign the informed consent before undergoing any specific study procedure that is not part of normal clinical practice.
  - 2 The patient must meet all the inclusion criteria and none of the exclusion criteria in order to be included in the study.
  - 3 Vital signs will be measured **every 8 hours** or every nursing shift until discharge: temperature, blood pressure, heart rate, respiratory rate, O2 saturation (including oxygenation method). Once the patient has been discharged, a single measurement of vital signs will be made at the study visits detailed in the table.
  - 4 The electrocardiogram will be performed during the baseline visit and on days 1, 2, 3, 4, 5, 6, 7, 15 and 31 from the start of treatment with plitidepsin. The PR interval and the QT interval will be measured.
  - 5 Complete blood count on days 1, 2, 3, 4, 5, 6, 7, 15 and 31.
  - 6 Basic biochemistry on days 1, 2, 3, 4, 5, 6, 7, 15 and 31. It will include transaminases, bilirubin, alkaline phosphatase, LDH, CK, ferritin and troponin.
  - 7 Coagulation on days 1, 2, 3, 4, 5, 6, 7, 15 and 31, including D-dimer.
  - 8 C-reactive protein on days 1, 2, 3, 4, 5, 6, 7, 15 and 31.
  - 9 The first time the patient tested positive for COVID-19 will be included as well. The test will be repeated in the 48 hours prior to administration of plitidepsin and on days 4, 7, 15 and 31, if negative detection does not occur before then. Qualitative PCR shall be obtained on nasopharyngeal exudate (preferably) or a sample from the lower respiratory tract.
  - 10 A chest X-ray will be performed at baseline and subsequently based on clinical discretion.
  - 11 Only fertile women.
  - 12 Patients may receive other pharmacological treatments for COVID-19 at the discretion of the investigator 24 hours after administration of the last dose of plitidepsin.
  - 13 Adverse events (serious and non-serious) will be recorded from signing of the informed consent up to 28 days after administration of the last dose of plitidepsin.
  - 14 A safety visit will be made 28 days (+3 days) after the last dose of plitidepsin.
  - 15 The viral load should be determined in a sample obtained from nasopharyngeal exudate (preferably) or a sample from the lower respiratory tract.

